#### 3.5.3.4.2 **BPI-SF**

The following pain intensity and pain interference scores (Cleeland, 2009) will be summarized and listed:

- From the eCRF, pain intensity recorded as "Worst", "Least", and "Average" in the last week and pain intensity recorded as "Right now".
- Composite pain severity score (a mean severity score of the above four pain items)

BRACHY-CHOR-001

- Composite pain interference score (a mean of the seven interference items). This will be calculated if at least four of the seven interference items have been completed on a given administration. Otherwise, the pain interference score will be considered missing.

For each subject, the worst observed score and the best observed score during the following periods will be summarized:

- Pre-Radiation Vaccination Period
- Radiation Therapy Period
- Post-Radiation Vaccination Period 1
- Post-Radiation Vaccination Period 2
- Overall Treatment Period

A score of 10 is the worst pain imaginable and a score of 0 is no pain. The worst score in each period is defined as the highest value within the period. The best score in each period is defined as the lowest value within the period.

Pain score category is defined for the "Worst" pain endpoint as 0 as no pain, 1-4 as mild pain, 5-6 as moderate pain and 7-10 as severe pain (Serlin, 1995).

For summary tables, the primary analysis will be performed on the EAS with additional analyses performed on the FAS. Continuous summary statistics will be provided for the worst observed score and the best observed score within each period for "Worst", "Least", "Average", and "Right Now" pain intensities as well as composite pain severity and composite pain interference scores. Individual pain interference items will be included in subject-level listings and will be plotted.

To explore if there is a correlation between tumor response and pain score, continuous summary statistics will be provided for the worst score within each period for "Worst", "Least", "Average", and "Right now" pain intensities as well as composite pain severity and composite pain interference scores by best overall tumor response per mRECIST. Similarly, a summary table will be provided for the best score within each period by best overall tumor response. Mean score and 95% CI will also be plotted over time by visit and by best overall tumor response for each BPI-SF item.

Additionally, a separate table will be presented for the number of subjects with improvement in "Worst" pain item and continuous summary statistics of the duration of improvement by best overall tumor response. Improvement in "Worst" pain item score is defined as a subject that has a reduction in pain score of 2 points from baseline and remains a reduction in pain score for at least 1 timepoint after the initial timepoint with pain reduction post-baseline (Cleeland, 2013). The duration of improvement is defined as the difference in weeks between the first timepoint of reduction in pain score of 2 points from baseline to the timepoint before an increase in pain of at least 2 points from the nadir value during the improvement time period. A Kaplan Meier figure will be provided for duration of improvement in the subset of subjects who experience pain improvement. The plot will be stratified by best overall response.

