#### **Secondary efficacy endpoints:**

- PFS by mRECIST 1.1 or irRC on target lesion(s)
- Improvement in clinical symptoms measured by the BPI-SF

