**BRACHY-CHOR-001** 

A separate table to summarize time to worsening in BPI-SF "Worst" pain item by best overall response will also be presented. A worsening in "Worst" pain item is defined as an increase in post-baseline pain score of at least 2 points and worsening in pain category among subjects who had no or mild pain at baseline and moderate or severe pain post-baseline or moderate pain at baseline and severe pain post-baseline. Time to worsening is defined the number of weeks in subjects who had at least a 2 point increase in pain and with no or mild pain at baseline to moderate or severe pain post-baseline or with moderate pain at baseline to moderate or severe pain post-baseline (Cleeland, 2013). A Kaplan Meier figure will be provided for the time to worsening in the subset of subjects who experience pain worsening and the figure will be plotted by best overall response.

To further explore the correlation between pain score and tumor response, worst observed BPI-SF scores by period and best observed BPI-SF scores will be summarized for subjects with any shrinkage in irradiated target lesions throughout the trial. Shrinkage in irradiated target lesions is defined as measurable lesions irradiated as part of trial treatment which decreased in length after baseline. Subjects are counted in the "Any shrinkage" category based on a decrease in the sum of the longest diameter of the irradiated target lesions of least a 5 mm. If there is no change, a decrease of less than 5 mm in the sum of the longest diameter of the irradiated target lesions or an increase in the sum of the longest diameter of the irradiated target lesions, subjects are counted in the "No shrinkage" category.

Shift tables of BPI-SF scores from baseline to worst observed values within each post-baseline periods and worst observed values in overall treatment period, and from baseline to best observed values within each post-baseline periods and best observed values in overall treatment period will also be presented by pain score categories for each BPI-SF item.

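### BPI-SF period scores are set against tumor response and lesion shrinkage as raw values, so differences in entry pain carry into these exploratory comparisons

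*SAP*

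**What the plan says.** The secondary efficacy endpoint in SAP section 1.5 is "Improvement in clinical symptoms measured by the BPI-SF". Section 3.5.3.4.2 then plans two kinds of analysis that link pain to tumor outcome.

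Raw-score analyses:
- By best overall response, the highest score per period: "To explore if there is a correlation between tumor response and pain score, continuous summary statistics will be provided for the worst score". This covers four intensity items and two composites.
- The lowest score likewise: "a summary table will be provided for the best score within each period by best overall tumor response".
- A plot: "Mean score and 95% CI will also be plotted over time by visit and by best overall tumor response for each BPI-SF item".
- By lesion shrinkage: "worst observed BPI-SF scores by period and best observed BPI-SF scores will be summarized for subjects with any shrinkage in irradiated target lesions".

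Baseline-referenced analyses:
- Improvement in the 'Worst' item, tabulated by best overall response and defined as a "reduction in pain score of 2 points from baseline and remains a reduction in pain score for at least 1 timepoint" after the first drop.
- Time to worsening in the 'Worst' item, also by best overall response, which requires "an increase in post-baseline pain score of at least 2 points and worsening in pain category".
- Shift tables from baseline for each item, with no split by response or shrinkage stated.

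The procedure schedules in both documents mark BPI-SF at Day 0 and not at Screening. The SAP General Definitions take baseline as the last value before first vaccination. They start the pre-radiation period, and hence the overall treatment period, on the date of first vaccination.

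**The concern.** Improvement needs a reference point, and these tables have none. Subjects are not randomised to being responders, and eligibility sets no pain level, so the groups may enter the trial with different pain. A raw post-baseline score carries that difference into every period. It also carries the full between-patient variance, which makes a real association harder to see.

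Elsewhere the SAP does use baseline. Target-lesion size is plotted as percent change (section 3.5.3.3.1), and ELISPOT results are given as a ratio to baseline (section 3.5.3.5).

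At stake is how the link between tumor response and patient-reported pain is read in a single-arm trial. Six scores, five periods, and worst and best values make 6 × 5 × 2 = 60 raw comparisons by response. An entry imbalance would tend to appear in many of them at once, because the scores belong to the same few subjects.

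**Working it through.** **1. How many responders.** The documents give no figure for the BPI-SF comparison itself, but the Simon design (SAP section 3.1) limits the group sizes. Its figures reproduce:
- Early termination at 5%: 0.95^10 = 0.599 (stated 60%).
- Expected sample size: 10 + (1 − 0.599) × 19 = 17.6 (stated 17.6).
- Type I error: sum over x ≥ 1 of P(x of 10) × P(at least 4 − x of 19) = 0.047 at 5% (stated at most 0.05). The same sum at 20% gives power 0.801 (stated 80%).

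Expected responders among 29 are 29 × 0.05 = 1.45 under the null and 29 × 0.20 = 5.8 under the alternative. Success needs 4. I therefore use 4 and 6.

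**2. Chance difference in entry pain.** SE = SD × √(1/n + 1/(29 − n)). The SD is assumed at 2.5 (range 2 to 3), since the documents give none.
- 4 v 25: 2.5 × √(1/4 + 1/25) = 1.35. P(difference ≥ 2 points) = 14% (6% at SD 2, 22% at SD 3).
- 6 v 23: 2.5 × √(1/6 + 1/23) = 1.15. P = 8% (3% to 15%).

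The shrinkage groups may be more even. At an assumed 14 v 15, SE = 2.5 × √(1/14 + 1/15) = 0.93 and P = 3%.

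**3. What reaches the planned table.** The SAP tabulates an extreme of several bounded scores, so this was simulated: 29 subjects, integer scores 0 to 10, mean 4, and worst of 4 visits (Post-Radiation Vaccination Period 1 has four scheduled visits). Response is unrelated to pain, and 20,000 trials were run per setting. The mean, the SD and the correlation between visits are assumptions. Chance of a group difference of at least 2 points at SD 2.5:

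| Responders | Correlation | Raw | Change from baseline | ANCOVA |
|---|---|---|---|---|
| 4 | 0.7 | 9.7% | 2.5% | 1.5% |
| 6 | 0.7 | 5.5% | 0.9% | 0.4% |
| 4 | 0.5 | 8.3% | 8.0% | 3.8% |

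With 4 responders over SD 2 to 3 and correlation 0.5 to 0.8, the ranges are raw 3% to 17%, change 0.1% to 13% and ANCOVA 0.1% to 7%.

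In the trials with 4 responders whose baseline means differ by 2 points or more by chance, the raw worst-score difference averages 1.2 to 2.1 points in the same direction. The ANCOVA difference averages about 0.

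**4. Precision.** With 4 responders, SD 2.5 and correlation 0.7, the SD of the estimated difference is 1.21 raw and 0.83 adjusted. The variance ratio is (0.83/1.21)² = 0.47, a fall of about 53%.

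**5. Do the baseline-referenced analyses close the gap?** Only partly. They cover one of the six scores. A subject entering at 0 or 1 cannot drop 2 points, and one already in the severe category cannot move to a worse one, so entry pain still decides who can count. The Kaplan-Meier figures include only subjects with the event. None of these analyses is by shrinkage.

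**6. Day 0 inside the period.** Because the pre-radiation and overall periods open on the first-vaccination date, the Day 0 score can itself be the period's worst or best value. Change in the worst score could then never be negative, and change in the best score never positive.

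**The case against.** A reader might infer that the SAP never uses baseline when it relates pain to response. It does: the 'Worst' item improvement and worsening analyses are baseline-referenced and tabulated by best overall response, and they bear most directly on the stated endpoint. That objection stands and limits the point to the raw tables, the plots and the shrinkage comparison.

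A reader might also infer that an entry imbalance would go unseen. It should not. A by-visit plot with Day 0 on the axis would show entry means by response group, scores are listed, and table layouts are left to a separate document. But seeing an imbalance is not removing it, and no plot by shrinkage category is planned.

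Third, 2 points is the SAP's threshold for one subject's change on one item, not a rule for group means. No test or success rule attaches to these tables, so the chance rates above are not error rates of any planned decision. That also stands; they serve only to give the size.

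Finally, modelling with 4 to 6 responders can look excessive in a descriptive display the SAP itself calls exploratory. This counts against reading the adjusted difference as inference. It does not count against showing baseline and change.

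**Conclusion.** The point holds for the period worst/best tables and mean plots by best overall response, and for the worst/best summaries by shrinkage category. In these, a chance or systematic difference in entry pain passes into the comparison. At SD 2.5 and correlation 0.7, a worst-score difference of 2 points or more arises by chance in about 5.5% to 10% of raw tables, against about 0.4% to 1.5% after adjustment. These figures rest on assumed SD, mean and correlation, on four visits, and on 4 to 6 responders; the shrinkage group sizes are unknown.

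The size is minor. The analyses are exploratory and descriptive, and the ORR decision does not depend on them. Adjustment deals with entry pain only. It does not make a comparison between response groups causal, and the estimates stay imprecise.

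**What to change.** In SAP section 3.5.3.4.2:
- Exclude the Day 0 pre-vaccination score from the worst and best values of the pre-radiation and overall treatment periods, and name it as the BPI-SF baseline.
- For the four intensity items and two composites, show the Day 0 score and the change from it beside the observed score, by best overall response and by shrinkage category.
- Give the mean difference (responder v non-responder, shrinkage v none) adjusted for the Day 0 score by ANCOVA, with 95% CI, labelled exploratory. The adjusted difference should carry the comparison, because at correlation 0.5 change alone gains almost nothing over the raw score (8.0% v 8.3%).

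The cost is SAP wording and a few more table columns, with no new data collection. Subjects without a Day 0 score drop out of the change and adjusted columns, so the number contributing should be shown.

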#### 4.3 Trial Duration

The total duration of trial for each patient is up to 29 months

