#### 3 Statistical Methods

## 3.1 Planned Sample Size

The null hypothesis that the true ORR anytime within 12 months after completion of radiation is 5% will be tested based on a one-sided alternative. In the first stage, 10 subjects will be accrued. If there are 0 responders in these 10 subjects, the trial will be terminated. If there is at least 1 responder in these 10 subjects, 19 additional subjects will be accrued for a total of 29 subjects. The null hypothesis will be rejected if 4 or more responses are observed in 29 subjects. This design retains a one-sided type I error rate of  $\leq 0.05$  and achieves 80% power when the true response rate is 20%.

The optimal design minimizes the expected sample size under the null hypothesis while satisfying the type I error and power constraint. With the above design, the probability of early termination is 60% and the expected sample size is 17.6 when the true response rate is 5% (under the null hypothesis).

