## 3.4.2 Data Handling Conventions for Efficacy Analyses

For PFS, if a subject has no date of death and has not progressed by the time of the analysis, the subject will be censored at the last radiologic assessment showing that no progression has occurred.

Subjects who have no record of CR/PR and withdraw early from the trial or are lost to follow-up will be considered as non-responders for the ORR analyses and will be considered to have progression for the by-time-point PFS analyses.

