## 3.5 Analysis and Presentation Methods

#### 3.5.1 General Presentation Methods

Categorical variables will be summarized using frequencies and percentage of subjects within each category, unless otherwise stated. Continuous variables will be summarized using the following statistics: mean, standard deviation, median, minimum, and maximum. Variables that are log normally distributed will be presented using geometric means and confidence intervals. Percentages will be presented to one decimal place. If a frequency is 0, the percentage will not be presented to draw attention to the non-zero cells of the tables.

For continuous statistics, precision will be based on the precision of the original data points. Means and medians will be presented to the original precision plus one decimal place. Standard deviations will be presented to the original precision plus two decimal places. The minimum and

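### The duration-of-pain-improvement table has no rule for subjects still improved at their last BPI-SF, so its plain summary statistics run short; state a censoring rule and report Kaplan-Meier estimates

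*SAP*

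**What the plan says.** SAP 3.5.3.4.2 (BPI-SF) defines improvement in the 'Worst' pain item as a 2-point drop from baseline, with the score still reduced at one or more later timepoints. Duration, in weeks, starts at "the first timepoint of reduction in pain score of 2 points from baseline" and runs "to the timepoint before an increase in pain of at least 2 points from the nadir value during the improvement time period". No other end is given.

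Two outputs use this duration:

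- A table with the number of improvers and "continuous summary statistics of the duration of improvement by best overall tumor response". SAP 3.5.1 fixes what that means: "Continuous variables will be summarized using the following statistics: mean, standard deviation, median, minimum, and maximum".
- A curve: "A Kaplan Meier figure will be provided for duration of improvement in the subset of subjects who experience pain improvement". It is stratified by best overall response.

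SAP 3.4.2 (data handling for efficacy) and 3.5.3.4.1 contain censoring rules, but only for PFS. In 3.4.2, a subject without death or progression is handled thus: "the subject will be censored at the last radiologic assessment showing that no progression has occurred". Nothing equivalent is written for pain duration. Follow-up is finite; Protocol 4.3 says "The total duration of trial for each patient is up to 29 months".

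**The concern.** Duration of relief is a right-censored quantity. Some improvers will complete the trial, leave at progression, withdraw or die without the 2-point rise that ends the clock. For them the definition returns no value, yet the table asks for a mean, SD, median, minimum and maximum, none of which allows for censoring. The programmer has to choose between two unwritten options:

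- **Drop** these subjects as missing, which removes the longest-lasting relief.
- **Cut off** at the last assessment and treat that time as a completed duration.

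The table is split by best overall response, and progression is a ground for leaving the trial (Protocol 4.2.6). Follow-up length may therefore differ between the groups being compared. A difference in tabulated duration between responders and non-responders could then partly reflect how long each group was observed.

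**Working it through.** **The plan's own figures.** The documents state no figure for duration of pain improvement. The only design figures belong to the primary test ("The null hypothesis that the true ORR anytime within 12 months after completion of radiation is 5% will be tested based on a one-sided alternative"). They reproduce: early stopping 0.95^10 = 0.599, expected N = 10 + 0.401 × 19 = 17.6, and exact two-stage type I error 0.0468 and power 0.801. None depends on the pain analysis.

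**Inputs from the documents.** Start and end of duration and the table statistics are as given in SAP 3.5.3.4.2 and 3.5.1. Maximum follow-up is 29 months from entry, about 29 × 30.44 / 7 = 126 weeks, so time left after improvement begins is shorter.

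**Assumed inputs.** Exponential time *T* to the qualifying rise, with true median *m* = 26, 52 or 104 weeks, and follow-up *C* after onset that is unrelated to *T*.

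**Formulas for a common *C*.** Let λ = ln 2 / *m*, S = exp(−λ*C*) (share with no end) and F = 1 − S.

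- Dropped: mean = (F/λ − *C*·S) / F; median = −ln(1 − F/2) / λ.
- Cut off: mean = F/λ; median = the smaller of *m* and *C*.
- Kaplan-Meier with censoring at *C*: median = *m* if *m* ≤ *C*, otherwise not reached.

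**Worked case, *m* = 52 and *C* = 52.** 1/λ = 75.0, S = F = 0.50. Cut-off mean = 0.50 × 75.0 = 37.5. Dropped mean = (37.5 − 52 × 0.50) / 0.50 = 23.0. Dropped median = 0.2877 × 75.0 = 21.6. Kaplan-Meier median = 52.

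| True median (mean) | *C* | No end | Dropped: mean / median | Cut off: mean / median | Kaplan-Meier median |
|---|---|---|---|---|---|
| 26 (37.5) | 26 | 50% | 11.5 / 10.8 | 18.8 / 26 | 26 |
| 26 (37.5) | 52 | 25% | 20.2 / 17.6 | 28.1 / 26 | 26 |
| 26 (37.5) | 104 | 6% | 30.6 / 23.7 | 35.2 / 26 | 26 |
| 52 (75.0) | 26 | 71% | 12.3 / 11.9 | 22.0 / 26 | not reached |
| 52 (75.0) | 52 | 50% | 23.0 / 21.6 | 37.5 / 52 | 52 |
| 52 (75.0) | 104 | 25% | 40.4 / 35.3 | 56.3 / 52 | 52 |
| 104 (150.0) | 26 | 84% | 12.6 / 12.4 | 23.9 / 26 | not reached |
| 104 (150.0) | 52 | 71% | 24.5 / 23.8 | 43.9 / 52 | not reached |
| 104 (150.0) | 104 | 50% | 46.0 / 43.2 | 75.0 / 104 | 104 |

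The mean is low in all nine cases on both paths, and for a given *C* the shortfall grows with the durability of relief. The dropped median is low throughout. The cut-off median is low only where fewer than half have ended.

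**Follow-up that varies between subjects.** With *C* uniform on 20 to 110 weeks (simulated), the share with no end is 22%, 45% and 66% for true medians 26, 52 and 104. The dropped median is about 18.5, 24 and 28; the cut-off median is about 24, 37 and 48. So when follow-up varies, the cut-off median also falls short where more than half have ended, by little in the mildest case (24 against 26). On the dropped path, a fourfold range of true medians shrinks to 18.5 to 28.

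**The case against.** The strongest reply is that the plan already contains the right tool. The sentences after the duration definition plan a Kaplan-Meier figure for the same endpoint, subset and stratification. With ordinary censoring, it keeps subjects with lasting relief at risk until their last assessment. A reader might infer that durable pain benefit is understated in the analysis as a whole. The documents do not support that: the shortfall is shown for the table's duration statistics, and the count of improvers in the same table does not use the end rule.

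This stands, with two limits. The figure's censoring rule is not written either, and ordinary censoring cannot simply be presumed: the companion time-to-worsening curve in the same section is confined to subjects who worsened, all of whom have the event. And a correctly censored figure would leave the table unchanged, so the two could show different medians for one endpoint.

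A second reply is that the table matters little. BPI-SF improvement is a secondary efficacy endpoint, but its main summaries are worst and best scores by period. The duration table is a descriptive addition with no test or success criterion, and subject-level listings will show individual data. This also stands, and limits the point's weight.

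Third, the table shells are in a separate document that was not available (SAP Appendix 2) and may show numbers ongoing. The SAP text does not.

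**Conclusion.** The point holds for the duration table. The definition has an end only for subjects who lose the improvement, the prescribed statistics do not suit a censored duration, and no rule covers the rest. The tabulated mean is biased low whichever unwritten choice is made. The median is low if subjects are dropped, or if they are counted as ended and fewer than half have truly ended; varying follow-up can also pull it down short of that.

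The direction rests on follow-up being unrelated to duration, and on some improvers still being improved at their last assessment. The size cannot be computed from the documents. The illustrations range from slight (a cut-off median of 24 against 26 weeks) to large (a dropped mean of 12.6 against 150.0 weeks), all under assumed durations and follow-up.

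A reader might also infer a known bias for or against responders. The documents do not support a direction, since neither durability nor follow-up by response group is given. The primary ORR test and the main BPI-SF summaries by period are unaffected.

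**What to change.** In SAP 3.5.3.4.2:

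1. State that improvers without a qualifying rise are censored at their last BPI-SF assessment, and apply this to both the table and the Kaplan-Meier figure.
2. Replace the plain duration statistics with the number of improvers, number ended, number censored by reason (completed, progression, withdrawal, death), and the Kaplan-Meier median with 95% CI.
3. Note that censoring at progression or death may be informative and could flatter durability. Add a sensitivity analysis that counts those events as end of improvement.

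The cost is a few sentences of SAP text, one revised table shell and one sensitivity run; no new data are needed. The downside is that medians may be not reached or imprecise: at most 29 evaluable subjects are planned for the primary evaluation, and the table covers only improvers, split by response.

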### 4.2.2.2 Evaluation of Response

Appropriate imaging with CT of the chest/abdomen/pelvis and MRI (if target lesion is best visualized by MRI) to reassess tumor extent and to determine tumor measurements will be performed 14 weeks after completion of radiotherapy and with each subsequent dose of vaccine thereafter (with windows for treatment as designated in the schedule of events, [Section 1.5](#)).

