#### 4.2.5 Withdrawal from Vaccination

Patients will be withdrawn from vaccination if any of the following is true:

- Target lesion disease progression as determined by
  - Radiographic disease progression by standard RECIST 1.1
  - Symptomatic disease progression by symptoms with concurrent evidence of any tumor enlargement
  - NOTE: A patient may continue on trial, at the investigator's discretion, with progression if he/she is eligible for local intervention for a non-target lesion progression
  - NOTE: A patient may remain on trial after initial evidence of target lesion disease progression until a confirmatory scan has been performed due to tumor swelling that can occur with radiotherapy and/or immunotherapy
- Patient withdrawal of consent (must document patient rationale for withdrawal)
- Positive pregnancy test
- Intercurrent illness or medical circumstances. If at any time the constraints of this protocol are detrimental to the patient's health, the patient may be removed from protocol therapy. In this event, the reasons for withdrawal will be documented.
- Adverse events meeting the following criteria: Evidence of any  $\geq$  Grade 3 allergic and  $\geq$  Grade 3 autoimmune reaction(s) attributed to vaccine (**except** Grade 3 endocrine-related immune toxicity or Grade 3 endocrine-related immune toxicity that resolves to Grade  $\leq$  1 clinically within 7 days of initiating supportive therapy); or if  $>$  Grade 2 toxicity attributed to vaccine persists for  $>$  28 days, the patient will not receive further vaccine injections. Patients who come off treatment must be followed on trial until resolution of toxicity and until disease progression.

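### Time to pain worsening is plotted among worseners only and split by best overall response, so longer follow-up of responders can pass for a pain benefit

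*SAP*

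**What the plan says.** SAP 3.5.3.4.2 plans two Kaplan-Meier figures for the worst-pain item, each with a matching table by best overall response.

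- **Time to worsening.** Only subjects with the event are plotted: "A Kaplan Meier figure will be provided for the time to worsening in the subset of subjects who experience pain worsening". On how the curves are split, the SAP says that "the figure will be plotted by best overall response". The definition reads "Time to worsening is defined the number of weeks in subjects who had at least a 2 point increase in pain". No time origin and no censoring rule are given. Since every subject in the plot has the event, nobody can be censored.
- **Duration of improvement.** Here too only a subset is plotted: "A Kaplan Meier figure will be provided for duration of improvement in the subset of subjects who experience pain improvement". The split is the same: "The plot will be stratified by best overall response". This clock runs "between the first timepoint of reduction in pain score of 2 points from baseline" to the visit before pain rises again. The table gives the number improved and continuous summary statistics of duration. It has no rule for improvements still ongoing at last contact.

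On response, Protocol 4.2.2.2 says imaging "will be performed 14 weeks after completion of radiotherapy and with each subsequent dose of vaccine thereafter". SAP 3.5.3.2 requires confirmation at least 4 weeks later.

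On follow-up, Protocol 4.2.6 ends participation at progression, and Protocol 4.2.3 takes subjects off trial after the 30-day visit. SAP 3.4.2 counts early leavers without CR or PR as non-responders for ORR. Pain tables use the EAS first and the FAS as an addition. The EAS requires at least one post-baseline scan (SAP 3.2).

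**The concern.** Best overall response is fixed after the pain clock has started. To be a responder, a subject must stay until a scan shows response and another confirms it. A non-responder need not stay that long. The two groups therefore differ in length of observation before pain is considered.

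A curve restricted to observed worseners turns that difference directly into a difference in time to worsening. Subjects followed briefly can enter the plot only if they worsen early. Subjects followed for long can also enter with late worsening.

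Improvement in BPI-SF is one of two secondary efficacy endpoints, and the SAP presents these displays as exploring whether response and pain are correlated. In a single-arm trial of 29 evaluable subjects, a visible separation could be read as evidence that tumour response brings pain benefit.

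**Working it through.** **The plan's own figures.** None are given for the pain displays. The Simon design in SAP 3.1 reproduces: type I error 0.0468, power 0.8011, early stopping 0.95^10 = 0.599, expected size 10 + 19 × (1 − 0.599) = 17.62. It plays no part below.

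**When response can exist.** The Day 28 dose is week 4, and radiotherapy starts 2 to 4 weeks later (SAP 1.1), in week 6 to 8. Its length is not fixed. I take 0 weeks (one fraction) to 8.6 weeks (50.4 + 27 = 77.4 Gy from Protocol 6.3.1.2, at 1.8 Gy throughout = 43 fractions, five a week assumed).

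- First scan: 6 + 0 + 14 = 20 to 8 + 8.6 + 14 = 30.6, so week 20 to 31.
- Confirmed 4 weeks later: week 24 to 35.
- Confirmed at the next scheduled scan, 12 weeks later: week 32 to 43.

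**Why the restriction matters.** Suppose worsening is exponential with rate λ and follow-up ends at c. The median among those who worsen by c is m(c) = −ln[1 − ½(1 − e^(−λc))]/λ. Assume a median of 52 weeks, so λ = ln 2/52 = 0.01333.

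- A subject progresses at 39 weeks (assumed, from the 9-month median PFS of a systemic-therapy trial in Protocol Table 1) and leaves about 30 days later. Then c = 43 and m = 18.5 weeks.
- A subject completes the schedule with radiation ending in week 11. Then c = 11 + 110 = 121 and m = 38.4 weeks.

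The hazard is the same in both. These are extremes that show the mechanism, not a forecast.

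**Simulation on the trial's visit schedule.** 60,000 subjects, with pain independent of response and progression. Assumed: 4 weeks of radiation; 20% latent response spread over the +14, +26, +38 and +50 week scans; median worsening 52 weeks; median progression 39 weeks; off trial about 30 days after progression.

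| Null scenario | Summary of worsening | Responders | Non-responders |
|---|---|---|---|
| Complete follow-up | Median, worseners only | 49 | 49 |
| Progression ends follow-up (EAS) | Median, worseners only, as in the SAP | 37 | 21 |
| Same | Mean, worseners only | 41.2 | 31.1 |
| Same | Share seen to worsen | 65% | 47% |
| Same | Kaplan-Meier median, all subjects, censored | 61 | 61 |
| Plus 25% leave at worsening | Worsening-free at End Radiation +26 weeks, EAS | 0.677 | 0.648 |
| Same | FAS | 0.677 | 0.605 |
| Plus 50% leave at worsening | EAS | 0.744 | 0.690 |
| Same | FAS | 0.744 | 0.599 |
| Landmark at End Radiation +30 weeks, 0, 25 or 50% leaving | Worsening-free 52 weeks later | 0.534 | 0.528 |

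The worseners-only medians become 25 against 17 with median worsening of 26 weeks, 49 against 25 with 104 weeks, and 37 against 25 with median progression of 60 weeks. Medians in this run fall on visit dates: with radiation ending in week 11, weeks 21 and 37 are the +10 and +26 week visits. The 16-week gap is therefore coarse, and the 10.1-week difference in means is steadier. A separate null simulation without pain-driven exit gives 33 to 36 against 25 to 31 weeks.

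**Rate ratios with all subjects included and censored.** Assumed: median worsening 52 weeks; 25% destined to respond at +14, +26 or +38 weeks and confirmed 12 weeks later; other dropout with median 60 or 120 weeks; radiation 0 to 9 weeks; exit 6 weeks after worsening.

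| Worseners who exit | No first scan required | First scan required, as in the EAS |
|---|---|---|
| 0% | 1.00 | – |
| 25% | 0.86 to 0.87 | 0.94 to 0.96 |
| 50% | 0.72 to 0.74 | 0.88 to 0.89 |

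If only subjects not destined to respond exit, from the first scan on, the ratio is 0.99 to 1.01. A landmark gives 0.98 to 1.02.

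**Duration of improvement (progression ends follow-up).** With ordinary censoring the Kaplan-Meier medians are 44 against 42 weeks. Uncensored means are 39.8 against 30.7 weeks, and 69% against 54% are seen to improve. With complete follow-up the means are 46.2 against 46.6 and the shares 78% and 79%. In 31% of improving responders the clock starts at or after the response scan.

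**The case against.** The strongest reply is that late classification alone does no harm. With complete follow-up, or with everyone included and censoring unrelated to pain, the null curves coincide. That stands: the gap needs unequal follow-up combined with a restricted or uncensored summary, or exit driven by pain.

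Second, the withdrawal rule does not link pain to non-response by itself. Protocol 4.2.5 lists "Symptomatic disease progression by symptoms with concurrent evidence of any tumor enlargement", so pain without enlargement does not trigger it. The same section also lets a subject stay until a confirmatory scan. This stands too. What remains is a subject choosing to leave because of pain (Protocol 4.2.6), at an unknown rate.

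Third, the EAS gives both groups the time to the first scan. That shrinks the pain-driven part but does not remove it, because one scan does not confirm a response and FAS tables are also planned. Nor does it help the worseners-only curve, where the 37 against 21 weeks is an EAS result.

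Fourth, the displays carry no test or alpha, and the main pain summaries by period are not split by response. This limits the consequence to interpretation.

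Fifth, a landmark would be very small in this trial. That is correct and bears on the fix.

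**Conclusion.** The point holds for the time-to-worsening display as written. Restricting it to worseners and splitting it by best overall response can produce a gap in favour of responders with no true association, about 33 to 37 weeks against 21 to 31 under the assumed inputs. It needs no pain-driven exit, only that progression or dropout shortens follow-up in non-responders. Correct risk sets and censoring remove it unless subjects leave when pain worsens. In that case the smaller gap in the rate-ratio table remains, and it is larger in the FAS than in the EAS.

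The duration-of-improvement curve is nearly unbiased once ongoing improvements are censored. Its uncensored means and the number improved are not.

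A reader might go further and infer that anyone whose pain worsens early is a non-responder by construction, or that these displays must show a link. The documents do not support that. A pain event does not by itself stop scanning, the symptomatic rule needs concurrent enlargement, and the null ratio is 1.00 when nobody exits because of pain.

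The sizes depend on assumed rates of worsening, progression, response and exit, and on two groups where the SAP may plot several response categories. The primary ORR test and PFS are untouched.

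**What to change.** In SAP 3.5.3.4.2:

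1. **Time to worsening.** Include all subjects at risk, that is, those whose baseline pain category can still worsen. Start at first vaccination and censor at the last BPI-SF.
2. **Response.** Treat it as time-dependent: a subject counts as a non-responder until the response scan and as a responder afterwards. Repeat with the switch at the confirming scan, because the interval between the two scans is again guaranteed to confirmed responders.
3. **Landmark.** Add a supportive display at the End Radiation +26 weeks scan. Fix response status there, include subjects still followed and event-free, show numbers at risk, and list those who left or worsened earlier.
4. **Duration of improvement.** Report the Kaplan-Meier median with ongoing improvements censored, not means of observed durations. Show follow-up time beside the number improved.

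The cost is SAP wording and reprogramming of two figures and two tables, with no new data. On the rate-ratio inputs above, the landmark set would hold about 11 to 14 of 29 subjects and 1 or 2 responders. It can only be descriptive, so the time-dependent analysis should lead.
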